13.2. ADVERSE EVENT SEVERITY

The severity of all AEs is assessed by the Investigator utilizing the following categories:

- **Mild:** The AE is transient and easily tolerated by the subject.
- **Moderate:** The AE causes the subject discomfort and interrupts the subject's usual activities.
- **Severe:** The AE causes considerable interference with the subject's usual activities and may be incapacitating or life-threatening, including those events resulting in a subject's disability or permanent damage, and/or required intervention to prevent permanent disability or damage.

- **Life-Threatening**: The AE results in a life-threatening illness or injury.
- **Fatal**: The AE results in death.

13.3. RELATIONSHIP TO THE DEVICE

Only events considered possibly, probably or definitely related to the device will be captured for this clinical investigation.

13.4. ADVERSE EVENT/INCIDENT REPORTING

In the event a SADE, UADE or serious incident occurs, the Investigator is required to notify the Sponsor within 48 hours of being made aware of the event. The Investigator also is required to notify their IRB in accordance with the policies of their local laws and regulations.

13.5. FORESEEABLE ADEs, SADEs and INCIDENTS

ADEs, SADEs and incidents which may be expected as part of the surgical intervention include:

- *Perioperative complications*
 - Malpositioning of the humeral or glenoidal component
 - Oversizing of implant components
 - Undersizing of implant components
 - Intraoperative fracture of the humerus or glenoid
 - Cement leakage, if applicable
 - Nerve injury, mild (minor motor or sensory loss, or spontaneous recovery)
 - Nerve injury, severe (significant motor or sensory loss or requiring surgical revision)
 - Vessel injury
 - Tendon injury
 - Wound complications (e.g. hematoma, wound healing disturbances)
 - Superficial infection
 - Deep infection
 - Deep vein thrombosis
 - Pulmonary embolism
- *Complications in the follow-up period*
 - Implant dislocation
 - Other subluxation or instability, symptomatic
 - Implant component dissociation, humeral head from humeral stem
 - Implant fretting or crevice corrosion
 - Implant breakage/wear, humeral or glenoidal
 - Implant loosening, humeral or glenoidal
 - Radiographic lucency, humeral or glenoidal
 - Rotator cuff tear
 - Pain related to the implant, severe
 - Late infection (e.g. hematogenous or protracted)
 - Periprosthetic fracture of the humerus or glenoid
 - Stiffness
 - Heterotopic ossification, asymptomatic or symptomatic
 - Healing disturbances of subscapularis tenotomy, if applicable
 - Non-union of lesser tuberosity osteotomy, if applicable
 - Malunion of lesser tuberosity osteotomy, if applicable

14. Reoperations

Reoperations and reason(s) for reoperations will be collected throughout the course of the clinical investigation. A reoperation may include but not limited to irrigation and debridement, revision surgery and/or implant removal.

15. Ethics

This clinical investigation is to be conducted according to International Conference of Harmonisation of Good Clinical Practice (ICH-GCP), applicable regulations, institutional research policies and procedures, Declaration of Helsinki and in compliance with the CIP. Investigators will be trained on the clinical investigation devices and surgical techniques prior to implanting clinical investigation subjects.

This CIP and any amendments will be submitted to a properly constituted independent ethics board, in agreement with local legal prescriptions, for formal approval of the clinical investigation conduct. The decision of the ethics board concerning the conduct of the clinical investigation will be made in writing to the Investigator before commencement of this clinical investigation. Clinical investigations shall not begin until the governing regulatory authority has provided full, unconditional approval. Off-label use of the ReUnion TSA System is not permitted.

15.1. INSTITUTION REVIEW BOARD (IRB)

IRB approval will be obtained at each of the investigational sites prior to enrolling clinical investigation subjects at that site. In addition, any SAEs and UADEs that meet the reporting criteria of the IRB, will be reported to the IRB. During the clinical investigation, the Investigator should promptly provide written reports to the IRB of any changes that affect the conduct of the clinical investigation and/or increase risk to the subjects, unless otherwise submitted by the Sponsor.

15.2. INFORMED CONSENT

The Investigator, or qualified clinical investigation personnel designated to perform this task, will explain the nature of the clinical investigation to the subject, and answer all questions regarding participation in this clinical investigation. Prior to any clinical investigation procedures being performed, the informed consent form (ICF) will be reviewed, signed and dated by the subject, and by the person administering the informed consent. A copy of the ICF will be given to the subject, and the original will be placed in the subject's clinical investigation records. Subjects will need to sign updated versions of the ICF if required by the Investigator's IRB during the clinical investigation.

16. Data Collection Process

The Sponsor will collect clinical data for this clinical investigation utilizing eCRFs through an EDC system. All data entered in the eCRFs are supported by source documentation. All clinical data is entered into the EDC system by designated personnel at each of the Investigator sites.

16.1. RADIOGRAPHS

All radiographs shall be de-identified of personal health information. Radiographs will be uploaded as DICOM images into the EDC system. The radiologic analysis shall be based at minimum on an axillary lateral radiograph and an anteroposterior radiograph. Additional radiographs (e.g., 30° to 40° posterior oblique radiographs in internal and external rotation) may be used where available. For measurements, all digital radiographs shall be sized to 100%, based on the diameter of the humeral head or other suitable reference sizes.

17. Clinical Investigation Monitoring

It is the responsibility of the Investigator to oversee the safety of the clinical investigation at his/her site, to include the careful assessment and appropriate reporting of AEs/incidents as noted above as well as the implementation of site data safety. The Sponsor, or designee will monitor the site to ensure informed consent has been documented appropriately, to ensure the information documented on the completed CRFs match the medical records and to resolve any differences. The Sponsor will take all steps necessary to ensure data integrity. The Sponsor also will review significant new information, including UADEs and ensure that such information is provided to all Investigators, their IRBs, and applicable regulatory authorities. Additionally, a quality assurance check will be performed to ensure the investigator is complying with the CIP and applicable regulations in the collection of all clinical investigation data.

18. Data Handling and Record Keeping

Information about clinical investigation subjects will be kept confidential. In the event a subject revokes authorization to collect or use protected health information, the Site Investigator, by regulation, retains the ability to use all information collected prior to the revocation of subject authorization. The Health Insurance Portability and accountability Act (HIPAA) will apply to ensure data protection and document anonymization. Records are to be stored in a secure location. Retention of records shall be maintained through the clinical investigation duration as well as specified years following the clinical investigation completion as required by local regulatory authority.

19. Reports

Analysis will be performed and interim reports will be prepared on a yearly basis. Upon the completion of all subjects' final post-operative assessment, data freeze will occur, and the final report will be prepared.

1.1. LIST OF ABBREVIATIONS

Acronym	Definition
ADE	Adverse Device Event
AE	Adverse Event
ASES	American Shoulder and Elbow Surgeons
CI	Confidence Interval
CIP	Clinical Investigation Plan
CRF	Case Report Form
eCRF	Electronic Case Report Form
EDC	Electronic Data Capture
FR	Final Report
ICF	Informed Consent Form
IFU	Instructions for Use
IR	Interim/Annual Report
IRB	Institutional Review Board
ITT	Intent-to-Treat
LTFU	Lost to Follow-Up
PP	Per Protocol
RSA	Reverse Shoulder Arthroplasty
SADE	Serious Adverse Device Effect
SAE	Serious Adverse Event
SAP	Statistical Analysis Plan
TFL	Tables, Figures, Listings
TSA	Total Shoulder Arthroplasty
UADE	Unanticipated Adverse Device Effect

1.2. STATISTICAL ANALYSIS PLAN REVISION HISTORY

Version	Effective Date	Description	Reason
1	27OCT2020	Initial Version	
2	28MAY2021	Distinction interim/final Analysis Amendment Table Templates section 7	Revision DQI 20-048

2.1. BACKGROUND AND RATIONALE

The ReUnion TSA System is designed as an anatomical total shoulder or hemi-shoulder endoprosthesis to address advanced arthritic disorders affecting the shoulder joint in subjects having intact or repairable rotator cuff function. The ReUnion TSA System consists of a completely modular shoulder platform including a Humeral Stem, Humeral Head and Glenoid. The intended purposes of the ReUnion TSA System are to achieve pain relief, improvement of range of motion and restoration or improvement of the shoulder function while ensuring long-term replacement of the shoulder joint with sufficient stability of all endoprosthesis components.

2.2. CLINICAL INVESTIGATION DESIGN

This investigation is a prospective, multicenter clinical investigation. It is anticipated that a total of one hundred (100) subjects will be enrolled at approximately 4-7 sites. Neither subjects nor investigators are blinded to treatment and the clinical investigation does not include a contemporaneous control. The clinical investigation has been designed to follow the surgeon's standard of care for shoulder arthroplasty subjects, which entails clinical evaluation on a regular ongoing basis, or as needed should the subject become symptomatic in the treated joint. The enrollment period is expected to occur over 14 months.

3. Research Goals

3.1. FRAMEWORK

All quantitative variables, including those based on calculations (secondary elements), will be analyzed with a case summary evaluation before the detailed characteristics and parameters can be evaluated. A case summary contains a listing of the number of valid cases/values, missing cases/values (if any) and total cases/values in the specific analysis. In general, a central position parameter for quantitative variables the mean, median and mode will be analyzed. As variation parameter the standard deviation, 95% confidence interval of the mean, interquartile range and range (based on maximum and minimum) will be calculated. All quantitative variables will be assessed for normality using the Shapiro-Wilk test. For optional visualization of quantitative variables, box-and-whisker plots will be used. Additional analyses like skewness and kurtosis measures or standard errors are optional also.

All qualitative variables, including those based on summaries (secondary elements), will be analyzed listing the proportions, frequencies, column and row totals, and missing proportion (if any).

3.1.1. Primary Analysis / Endpoint

The objective of the clinical investigation is to demonstrate non-inferiority (equal or better) of the ASES Shoulder Score in relationship to the officially cleared indications in comparison to respective clinical outcome data in the scientific literature.

[figure not shown]
Data collection of ASES Shoulder Score will start pre-operatively and will be collected according to schedule in Table 4.4. This will be repeated annually in all subjects who have the total or partial prosthesis with full or partial implant survival (including all subjects without removal of all endo-prosthesis components).

The 24 months postoperative results for subjects implanted with ReUnion TSA System will be compared to a historical group and results reported by respective clinical outcome data in the scientific literature. The benchmark sources and values will serve as the control group for the ReUnion TSA System subjects.

Higher ASES Shoulder Score results are linked to better subject results and vice versa.

The clinical investigation endpoint is non-inferiority to the control, meaning the clinical investigation result should be equal or better than the control. In this clinical investigation, an equal or better ASES Shoulder Score result means equal or more (\geq). As only results from samples will be captured, results mostly are estimates of the true population parameter. These estimates vary by a certain area, where it is expected that the true population parameter falls within. Based on this, it is required to specify a lower limit for the acceptable difference or zone of indifference, denoted as $-\theta$.

Hypotheses were developed to allow for a comparison of the 24 months postoperative ASES Shoulder Score effectiveness / performance between the two underlying populations. The 24 months postoperative ASES Shoulder Score is the primary endpoint of this clinical investigation. Hypothesis tests will be one-sided with a significance level α of 5%.

Hypothesis	Equations	Interpretation
Null (H0)	$A - B < -\theta$	Central tendency of A is inferior to the central tendency of B.
	ReUnion TSA System – Control (Benchmark) $< -\theta$	
Alternative (H1)	$A - B \geq -\theta$	Central tendency of A is non-inferior to the central tendency of B.
	ReUnion TSA System – Control (Benchmark) $\geq -\theta$	
		
Possible Evidence (p)	Possible Decisions	Possible Conclusions – ASES Shoulder Score

p-value > α (0.05)	Fail to reject null hypothesis (H0)	ReUnion TSA System < Control (Benchmark) Insufficient evidence to reject the null hypothesis (H0: A - B < - θ) at the pre-determined significance level of 5%.
p-value \leq α (0.05)	Reject null hypothesis (H1)	ReUnion TSA System \geq Control (Benchmark) Sufficient evidence to reject the null hypothesis (H0: A - B < - θ) at the pre-determined significance level of 5%.

Table 3.1.1: Research Goal and Hypothesis (Primary Endpoint)

To test non-inferiority, the 24 months mean ASES Shoulder Score result of the ReUnion TSA System group will be compared to the mean estimate of the control group, 82.16 points.

To be able to identify an acceptable difference or zone of indifference ($-\theta$), the pooled standard deviation of the ASES Shoulder Score result at 24 months postoperative in the control group (Benchmark) was used as lower limit (pooled standard deviation of control is 16.76 points). The lower maximum acceptable difference ($-\theta$) is 65.40 points (mean of control - θ or 82.16 – 16.76 = 65.40 points).

Based on the underlying distribution of the data and the result of the normality assessment, either the parametric one-sample t-test or the non-parametric one-sample sign test will be used to compare the 24 months postoperative ASES Shoulder Score results of the ReUnion TSA System against the value of 65.40 points.

The analysis of the primary endpoint / objective will be conducted when all subjects have completed the 24 months postoperative including the ASES Shoulder Score.

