	
  
 	Cases	
 
 	Valid	Missing	
 
 	N	Percent	N	
   
 		
 
 		
 
 		
  
						Cases					Valid		Missing			N	Percent	N												
		Cases																													
		Valid		Missing																											
		N	Percent	N																											
				Total																											
		N	Percent	N																											
Mean ASES ReUnion_TSA_CER		10	100,0%	0	0,0%																										
Std.Dev. ASES ReUnion_TSA_CER		7	70,0%	3	30,0%																										
					10																										
					100,0%																										

 | | | |

Descriptives						
			Statistic			
Std.Dev. ASES ReUnion_TSA_CER			16,7571			
Mean 95% Confidence Interval for Mean			Lower Bound 12,6353 Upper Bound 20,8790			
Median Std. Deviation Minimum Maximum Interquartile Range			16,7000 4,45678 10,10 22,40 7,90			
Mean ASES ReUnion_TSA_CER			82,1600			
95% Confidence Interval for Mean			Lower Bound 76,2372 Upper Bound 88,0828			
Median Std. Deviation Minimum Maximum Interquartile Range			81,5000 8,27945 64,00 94,40 9,40			
						
Red line: Pooled mean ASES Blue lines: 95% CI of pooled mean ASES Black line: Pooled median pooled ASES Box: Interquartile Range Green Line: Pooled mean ASES minus pooled std. dev. ASES (16.76) $82.16 - 16.76 = \mathbf{65.40 \text{ points}}$						
Acceptance Criteria for Sample Size Calculation						
Significance Level (α)	0.05 (5%)					
Power (1-β)	0.80 (80%)					
Confidence Interval (CI)	0.95 (95%)					
Tails	2					
Path	Non-inferiority – ReUnion TSA (A) \geq Benchmark (B, explorative meta-analysis in this document)					
Hypotheses Pair	Null (H_0)		A – B $< -\theta$			
	Alternative (H_1)		A – B $\geq -\theta$			
Benchmark Timepoint	24 months post-operative					
Benchmark n (sources)	10					
Benchmark Mean	82.16 (pooled mean ASES [points])					
Benchmark Std. Dev.	16.76 (pooled std. dev. ASES [points])					
Benchmark Value	Pooled mean ASES minus pooled std. dev. ASES (16.76)					
Non-Inferiority Margin (-θ)	$82.16 - 16.76 = \mathbf{65.40 \text{ points}}$					
Software Used	IBM SPSS Sample Power V3.0					
IBM SPSS Sample Power Output						

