p-value $> \alpha$ (0.05)	Fail to reject null hypothesis (H_0)	ReUnion TSA System $<$ Control (Benchmark) Insufficient evidence to reject the null hypothesis ($H_0: A - B < -\theta$) at the pre-determined significance level of 5%.
p-value $\leq \alpha$ (0.05)	Reject null hypothesis (H_1)	ReUnion TSA System \geq Control (Benchmark) Sufficient evidence to reject the null hypothesis ($H_0: A - B < -\theta$) at the pre-determined significance level of 5%.

To test non-inferiority, the 24 months mean ASES Shoulder Score result of the ReUnion TSA System group will be compared to the mean estimate of the control group, 82.16 points.

To be able to identify an acceptable difference or zone of indifference ($-\theta$), the pooled standard deviation of the ASES Shoulder Score result at 24 months post-operative in the control group (Benchmark) was used as lower limit (pooled standard deviation of control is 16.76 points). The lower maximum acceptable difference ($-\theta$) is 51.87 points (mean of control - θ or 82.16 - 16.76 = 65.40 points).

Based on the underlying distribution of the data and the result of the normality assessment, either the parametric one-sample t-test or the non-parametric one-sample sign test will be used to compare the 24 months post-operative ASES Shoulder Score results of the ReUnion TSA System against the value of 65.40 points.

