	95% Confidence Interval for Mean	Lower Bound	76,2372					
		Upper Bound	88,0828					
	Median	81,5000						
	Std. Deviation	8,27945						
	Minimum	64,00						
	Maximum	94,40						
	Interquartile Range	9,40						
								
Red line: Pooled mean ASES Blue lines: 95% CI of pooled mean ASES Black line: Pooled median pooled ASES Box: Interquartile Range Green Line: Pooled mean ASES minus pooled std. dev. ASES (16.76) $82.16 - 16.76 = \mathbf{65.40 \text{ points}}$								
Acceptance Criteria for Sample Size Calculation								
Significance Level (α)	0.05 (5%)							
Power (1- β)	0.80 (80%)							
Confidence Interval (CI)	0.95 (95%)							
Tails	2							
Path	Non-inferiority – ReUnion TSA (A) \geq Benchmark (B, explorative meta-analysis in this document)							
Hypotheses Pair	Null (H_0)	$A - B < -\theta$						
	Alternative (H_1)	$A - B \geq -\theta$						
Benchmark Timepoint	24 months postoperative							
Benchmark n (sources)	10							
Benchmark Mean	82.16 (pooled mean ASES [points])							
Benchmark Std. Dev.	16.76 (pooled std. dev. ASES [points])							
Benchmark Value Non-Inferiority Margin (- θ)	Pooled mean ASES minus pooled std. dev. ASES (16.76) $82.16 - 16.76 = \mathbf{65.40 \text{ points}}$							
Software Used	IBM SPSS Sample Power V3.0							
IBM SPSS Sample Power Output								
One goal of the proposed clinical investigation is to test the null hypothesis that the population mean is 82.16 points. The criterion for significance (alpha) has been set at 0.05. The test is 2-tailed, which means that effects in both directions will be interpreted. With the proposed sample size of 10 cases, the clinical investigation will have power of 80.3% to yield a statistically significant result. This computation assumes								

that the population from which the sample will be drawn has a mean of 82.16 points with a standard deviation of 16.76 points. The observed value will be tested against a theoretical value (constant, non-inferiority margin) of 65.40 points.

IBM SPSS Sample Power Output – Screenshot

Estimated overall drop-out rate is 56% which leads to the requirement of enrolling additional 6 subjects into the clinical investigation.

Sample Size	Number of subjects to be enrolled: 16 subjects (rounded up to 20 subjects)
Overall Sample Size (multiplied by number of indications (=5)	100 subjects

Table 3.2: Sample Size Justification

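### The hypothesis concerns A − B between two populations, but the one-sample test treats the estimated benchmark as known, so the 5% applies only to a fixed goal of 65.40

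*SAP*

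**What the plan says.** SAP 3.1.1 and Protocol 11.3.2 write H0 as A − B < −θ and H1 as A − B ≥ −θ, where A is the device and B the literature benchmark. SAP 3.1.1 says the hypotheses allow a "comparison of the 24 months postoperative ASES Shoulder Score effectiveness / performance between the two underlying populations", and sets the test one-sided at 5%.

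The same section describes the device mean as being "compared to the mean estimate of the control group, 82.16 points", so the plan itself calls 82.16 an estimate. Protocol Table 2 gives its 95% confidence interval: "Lower Bound 76,2372 Upper Bound 88,0828". The allowance θ is one benchmark SD ("pooled standard deviation of control is 16.76 points"), which leads to 82.16 − 16.76 = 65.40.

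The only primary test in either document is a one-sample t-test or, for non-normal data, a one-sample sign test. SAP 3.1.1 says that one of these "will be used to compare the 24 months postoperative ASES Shoulder Score results of the ReUnion TSA System against the value of 65.40 points". Protocol 11.3.2 likewise compares the "results of the ReUnion TSA System against the value of 65.40 points", and SAP 6.6 repeats this. The sample-size text in both documents calls 65.40 a constant. It also says "The test is 2-tailed, which means that effects in both directions will be interpreted", which conflicts with the one-sided 5%.

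**The concern.** The hypothesis and the test answer different questions. A one-sample test against 65.40 asks whether the device's population mean exceeds a given number. The stated hypothesis asks whether it lies within 16.76 points of the mean of another population. That second mean is known only from ten studies whose reported means run from 64 to 94.4.

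At the enrolment planned, the benchmark's standard error is at least as large as the device group's own. Leaving it out makes the p-value and lower confidence limit too optimistic for A − B. The effect grows with the number of evaluable subjects, because only the device group's error shrinks.

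**Working it through.** **Inputs.** Ten source means, their SD of 8.279 and the interval 76.24 to 88.08 (Protocol Table 2, SAP Table 3.2); ASES SD and θ of 16.76; one-sided 5% (SAP 3.1.1); 100 enrolled; 56% overall drop-out. No drop-out rate at 24 months is given. I assume 44 to 100 evaluable, where 44 = 100 × (1 − 0.56).

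**The plan's own figures.** The ten means give 82.16, SD 8.279 and 95% CI 76.24 to 88.08. The seven reported SDs average 16.757. Power for n = 10 by the noncentral t (df 9, noncentrality √10 × 16.76/16.76 = 3.162, two-sided 5%) is 80.3%, as stated. That calculation treats 65.40 as fixed. One-sided 5% would give 89.8%.

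**Benchmark error.** SE(B) = 8.279/√10 = 2.618. The printed interval gives the same: half-width 5.923 divided by t(0.975, 9 df) = 2.262.

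**Error for A − B.** Take the boundary, where the true A − B equals −16.76. With SE(A) = 16.76/√n, the one-sample test rejects with probability

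1 − Φ(1.645 × SE(A) / √(SE(A)² + SE(B)²)).

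| n evaluable | SE(A) | Total SE | One-sided error |
|---|---|---|---|
| 44 | 2.527 | 3.639 | 12.7% |
| 64 | 2.095 | 3.353 | 15.2% |
| 80 | 1.874 | 3.220 | 16.9% |
| 100 | 1.676 | 3.109 | 18.8% |

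Simulating the t-test itself (400,000 replicates per n) gives 12.5% at 44 and 18.6% at 100.

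**How far this depends on the setting.** One item is changed at a time.

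| Setting | Error, n = 44 to 100 |
|---|---|
| t-test, one-sided 5%, SE(B) 2.618 | 12–19% |
| Sign test (exact, normal scores simulated) | about 9–14% |
| Two-tailed 5%, so 2.5% per side | 8.7–14.5% |
| Random-effects SE(B) of 2.33 (SD 16.76 assumed for the three sources without one) | 11–17% |
| Within-study error only, SE(B) 0.69–0.79 | 5.6–6.9% |
| n = 10, the calculated sample size | about 7% |

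The sign-test figures do not rise smoothly, because the test is discrete: 10.0% at 44, 9.1% at 64 and 14.3% at 100. The within-study row does not fit the listed data, since I² among the ten sources is about 91%.

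**Effect of carrying SE(B).** The Satterthwaite df are (total SE)⁴ / [SE(A)⁴/(n − 1) + SE(B)⁴/9], which gives 28.4 at n = 44 and 17.6 at n = 100. The critical values are 1.700 and 1.736.

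- n = 44: the observed mean needed to pass moves from 65.40 + 1.645 × 2.527 = 69.6 to 65.40 + 1.700 × 3.639 = 71.6.
- n = 100: it moves from 65.40 + 1.645 × 1.676 = 68.2 to 65.40 + 1.736 × 3.109 = 70.8.
- Power at a true mean equal to the benchmark stays above 99% (99.8% at n = 44).

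**The case against.** The strongest reply is that the plan fixes 65.40 in advance, calls it a constant, and uses it in every statement of the test and in the power calculation. A performance goal taken from the literature is an accepted convention, and against that goal the one-sample t-test holds 5%. This stands. A reader might infer that the trial's real false-positive rate is 12–19%. The documents do not support that as a plain fact: the figure arises only if the literature set is treated as a random draw and the claim is about A − B. What the reply does not explain is why the hypotheses, the description of the comparison and the conclusion are all written for A − B.

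It can also be said that 12–19% is one setting among several. That stands too. Source 10 (mean 64, total and hemi-arthroplasty combined) adds much of the spread. Without it SE(B) would be about 1.87 and the error about 9–14%, although hemi-arthroplasty is within the system's scope.

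Finally, the outcome would seldom change. The decision differs only for observed means of roughly 69.6 to 71.6 (n = 44) or 68.2 to 70.8 (n = 100). With a true mean of 82.16, a mean below 71.6 at n = 44 has a chance of about 1 in 70,000. The leniency of the test comes mainly from the 16.76-point allowance. This limits the practical weight of the point but does not make the stated error rate apply to the stated hypothesis.

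**Conclusion.** The mismatch is real and appears in both documents. As written, the 5% belongs to the hypothesis that the population mean is at most 65.40 and not to A − B.

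For A − B the t-test's one-sided error would be about 12–19%. That rests on four conditions: 44 to 100 evaluable at 24 months, one-sided 5%, the documents' between-source standard error, and repeated sampling of both benchmark and trial. The sign-test, two-tailed and random-effects settings put it between about 9% and 17%, and n = 10 at about 7%.

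A reader might also infer that adding the benchmark error would justify the tabulated conclusion that the device is equal to or better than control. It would not. Rejecting H0 shows only that the device is not worse by more than 16.76 points. That is a separate matter of the margin.

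**What to change.** **Preferred.** In Protocol 11, 11.1 (Table 2) and 11.3.2, and in SAP 3.1.1, 3.2 (Table 3.2) and 6.6:

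- Restate H0 as population mean ≤ 65.40, or population median ≤ 65.40 if the sign test is used, and describe 65.40 as a fixed performance goal derived from the literature.
- Remove the A − B equations and the two-population wording.
- Limit the conclusion to whether the goal was met, and align the endpoint wording in Protocol 8.1.
- State one sidedness throughout.
- Add a sensitivity analysis, whichever primary test is used: the estimate of A − B with its lower confidence limit, from √(s²/n + 2.62²) with Satterthwaite df.

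**Alternative.** Keep A − B and make (mean − 65.40)/√(s²/n + 2.62²), with Satterthwaite df, the primary test. It has no direct sign-test counterpart, so the plan must then say what is done with non-normal data.

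**Cost.** Wording in two documents and one added analysis, with no extra subjects. The preferred route narrows the claim. The alternative raises the observed mean needed to pass by about 2.0 points at n = 44 and 2.6 at n = 100, with little loss of power.
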